#### **10.1.5 Neurovirulence Data**

Neurovirulence data will be obtained from the transgenic mouse assay applied to virus isolated from select stool samples **in this study. Assessment in the mouse neurovirulence model requires a minimally sufficient quantity of virus ( $\geq 4.0$  log10 CCID50 per gram) to be present in stool samples. Data from each sample tested will be summarized by group. For each candidate separately (2018 lots), if 5 or more such samples are available for 1 to 5 year-old and/or infant cohorts as well as from corresponding cohorts from the historical control study M2, these data** will be combined in order to directly compare the neurovirulence of samples from candidate vaccines to the control vaccine. **Additional assessment of samples from Stage I using candidate 2 (2016)** may also be performed. The proportion of mice paralyzed and the odds ratio of paralysis from the single-dose assay will be the primary means of comparison of NV of shed virus between each candidate and the Sabin mOPV2 control samples. The statistical hypothesis that will be tested will be that of superiority (lower neurovirulence) of at least one **2018 lot of candidate vaccine to Sabin 2**, with respect to the frequency of mouse paralysis observed in the assay. Exploratory analysis of additional samples, or samples from additional groups will also be considered.

The SAP will provide additional detail on the selection of samples, as well as the summary and comparison of these data.

#### **10.1.6 Safety Data**

For an overview of primary and secondary endpoints, see Section 3.

Safety parameters will be tabulated and analyzed descriptively, in the safety population, according to the actual vaccine received.

### ***Adverse Events***

Analyses described below will be performed for solicited and unsolicited AEs by severity using the Common Terminology Criteria for Adverse Events (CTCAE) version 4.03 published by NIH in 2010, as well as for SAEs and IMEs.

The original terms used in the designated sections of the eCRFs by Investigators to identify AEs will be fully described and coded according to the Medical Dictionary for Regulatory Activities (MedDRA).

All AEs will be summarized by time-point, group, severity and occurrence in relation to vaccination, and overall. Determination of causal association to the study vaccines will be assigned using the new individual causality assessment algorithm published by WHO in 2013. All SAEs and severe AEs will be deemed eligible for causality assessment by the investigator or the safety monitor. After applying the Adverse Event Following Immunization (AEFI) causality algorithm, the SAE or severe AE will be classified as consistent or inconsistent with causal association to immunization; those which meet the definition of causality will be defined as Serious Adverse Reactions (SAR). Those SAE or severe AEs with insufficient or conflicting evidence to make a determination of association will be deemed indeterminate according to the algorithm.

Separate tables and listings will be created for subjects who died, discontinued the study vaccine due to an AE, or experienced a severe or serious AE. Summaries, listings, and narratives may be provided, as appropriate. Unsolicited adverse events occurring within 28 days of any vaccine administration will be summarized, as will any data obtained on SAEs or IMEs reported during the extended safety follow-up or obtained in the follow-up telephone call at the end of the study.

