## **LIST OF ABBREVIATIONS AND DEFINITIONS OF TERMS**

### **List of Abbreviations**

AE	Adverse event
AEFI	Adverse event following immunization
ALT	Alanine aminotransferase
AR	Adverse reaction (AE related to vaccination)
AST	Aspartate aminotransferase
CCID 50	50% cell culture infective dose
CI	Confidence interval
CK	Creatine kinase
CRF	Case Report Form
CTCAE	Common Terminology Criteria for Adverse Events
DNA	Deoxyribonucleic acid
DSMB	Data Safety Monitoring Board
eCRF	Electronic Case Report Form
EDC	Electronic Data Capture
GCP	Good Clinical Practice
GGT	Gamma-glutamyltransferase
HBsAg	Hepatitis B surface antigen
HCV	Hepatitis C virus
HIV	Human immunodeficiency virus
ICF	Informed Consent Form
ICH	International Conference on Harmonization
IEC	Independent Ethics Committee
IME	Important Medical Event
IMP	Investigational medicinal product
IMR	Important Medical Reaction (IME related to vaccination)
IPV	Inactivated poliovirus vaccine
IRB	Institutional Review Board
LSLV	Last Subject Last Visit
MedDRA	Medical Dictionary for Regulatory Activities
mOPV2	Monovalent oral poliovirus vaccine type 2
nOPV2	Novel oral poliovirus vaccine type 2
OPV	Oral poliovirus vaccine
PD50	50% paralytic dose
PP	Per-protocol
RNA	Ribonucleic acid
SAE	Serious adverse event
SAP	Statistical Analysis Plan
SAR	Serious Adverse Reaction (SAE related to vaccination)
SD	Standard deviation
SmPC	Summary of Product Characteristics
SUSAR	Suspected Unexpected Serious Adverse Reaction
bOPV	Bivalent oral poliovirus vaccine
mOPV	Monovalent oral poliovirus vaccine
TgPVR	Transgenic mice expressing the cell receptor for poliovirus
TMF	Trial Master File
VAPP	Vaccine-associated paralytic poliomyelitis

CLINICAL STUDY PROTOCOL – M5

Amendment 2

4 March 2019 (Version 3.0)

WHO

World Health Organization

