### **3. STUDY ENDPOINTS**

#### **3.1 PRIMARY ENDPOINTS**

The following endpoints will be evaluated by group and overall:

- Safety: incidence of Serious Adverse Reactions (SAR), severe AR and IMR, i.e. SAEs, severe AEs (grade 3), or IMEs considered consistent with a causal association with study vaccines as of the informed consent signature date and throughout the study period in all groups.
- Immunogenicity: seroprotection rate of type 2 polio neutralizing antibodies at Day 28 following a single  $10^5$  or  $10^6$  CCID50 dose of nOPV2 candidates in all groups. Seroprotection rate is defined as the percentage of subjects with type 2-specific antibody titers  $\geq 1:8$  per group.

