### 11.2.2 *Unsolicited Adverse Events*

The investigator will assess the incidence and maximum intensity that occurred over the duration of the event for all unsolicited AEs recorded during the study. The assessment will be based on the investigator’s clinical judgment.

The intensity should be assigned to one of the following categories:

- 1 (mild) = An AE which is easily tolerated by the subject, causing minimal discomfort and not interfering with everyday activities.

[figure not shown]
- 2 (moderate) = An AE which is sufficiently discomforting to interfere with normal everyday activities.
- 3 (severe) = An AE which prevents normal, everyday activities (In adults, such an AE would, for example, prevent attendance at work and would necessitate the administration of corrective therapy.)

An AE that is assessed as Grade 3 (severe) should not be confused with a SAE. Grade 3 is a category used for rating the intensity of an event; and both AEs and SAEs can be assessed as Grade 3. An event is defined as ‘serious’ when it meets one of the pre-defined outcomes as described in Section 11.1.3.

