### 11.3 CAUSALITY ASSESSMENT

The investigator is obligated to assess the relationship between investigational vaccine and the occurrence of each AE/SAE/IME. The investigator will use clinical judgement to determine the relationship. Alternative plausible causes, such as natural history of the underlying diseases, concomitant therapy, other risk factors, and the temporal relationship of the event to the investigational vaccine will be considered and investigated. The investigator will also consult the Investigator’s Brochure to determine his/her assessment.

Causality should be assessed by the investigator using AEFI causality algorithm developed by WHO for individual AEFI evaluation. When appropriate information is available the investigator should arrive to the following possible conclusions:

\*B1 : Potential signal and maybe considered for investigation

Serious Adverse Events (SAE) considered to be causally related to the vaccination will be termed Serious Adverse Reactions (SAR).

If an event meets the criteria to be determined as ‘serious’ (see Section 11.1.3), additional examinations/tests will be performed by the investigator in order to determine ALL possible contributing factors for each SAE.

Possible contributing factors include:

- Medical history.
- Other medication.
- Protocol required procedure.
- Other procedure not required by the protocol.
- Lack of efficacy of the vaccine, if applicable.
- Erroneous administration.
- Other cause (specify).

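### Section 10.1.6 labels every causally related severe adverse event a Serious Adverse Reaction, which contradicts the endpoint definition and Section 11.3 and shifts events from the severe AR row to the SAR row

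*Combined protocol and SAP*

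**What the plan says.** **Analysis section.** Section 10.1.6 (Adverse Events) makes all SAEs and severe AEs eligible for causality assessment. After the algorithm, "the SAE or severe AE will be classified as consistent or inconsistent with causal association to immunization". Of these, "those which meet the definition of causality will be defined as Serious Adverse Reactions (SAR". For the remainder, SAEs and severe AEs "with insufficient or conflicting evidence to make a determination of association will be deemed indeterminate according to the algorithm". The section has no sentence that assigns a related but non-serious severe event to a severe AR category.

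**Definitions elsewhere.**
- Section 11.3: "Serious Adverse Events (SAE) considered to be causally related to the vaccination will be termed Serious Adverse Reactions (SAR".
- List of Abbreviations, under SAR: "Serious Adverse Reaction (SAE related to vaccination".
- Section 11.2.2: "An AE that is assessed as Grade 3 (severe) should not be confused with a SAE". It adds that seriousness depends on the outcomes listed in Section 11.1.3.

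**Endpoint.** Section 3.1 (and the Synopsis, Criteria for Evaluation) lists SAR, severe AR and IMR side by side. It matches them to SAEs, grade 3 AEs and IMEs "considered consistent with a causal association with study vaccines". Section 2.1 makes this a co-primary objective, to be contrasted with historical study M2.

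**The concern.** The analysis section and the endpoint section use the same label for different sets of events. A programmer who follows Section 10.1.6 will place every related grade 3 event in the SAR row. Under Table 1 of Section 11.2.1, a fever above 39.0°C is grade 3. It is not serious unless it also meets a criterion in Section 11.1.3.

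Severe but non-serious events are realistic here. Section 1.2 reports severe AST and CK elevations in the adult study M4a alongside no serious adverse events, and Section 11.1.1 counts abnormal laboratory findings as adverse events. The protocol considers exercise the likely explanation in those adults, so they show only that this kind of event occurs. They do not establish a rate in children.

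At stake is the reading of a co-primary result. A SAR rate is understood as a rate of serious reactions. If it silently includes non-serious events, it overstates them and the severe AR row understates its own. The contrast with M2 would also mislead if M2 used the narrower definition; the documents do not say how M2 coded these events.

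**Working it through.** **1. The plan's own safety figure.** Section 10.2 sizes the safety evaluation for a 90% chance of seeing at least one event at a true rate of 5%.
- 1 − 0.95^45 = 0.9006, while n = 44 gives 0.895, so 45 is the minimum.
- 45 / (1 − 0.10) = 50.

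Both figures reproduce. Neither depends on the SAR label.

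**2. Where each event goes.**

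| Event, classed as consistent | Sections 3.1, 11.3, Abbreviations | Section 10.1.6 read literally |
|---|---|---|
| SAE | SAR | SAR |
| Non-serious grade 3 AE | severe AR | SAR |
| IME | IMR | not mentioned in the classification sentence |

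**3. Effect on counts.** Let s be the related SAEs and v the related non-serious severe AEs.
- Section 11.3: SAR = s, and under Section 3.1 severe AR = v.
- Section 10.1.6: SAR = s + v and severe AR = 0.
- Combined: s + v under both.

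The documents give no rates for such events, so the counts below are assumptions.

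| s | v | SAR, 11.3 | Severe AR, 3.1 | SAR, 10.1.6 | Severe AR, 10.1.6 | Combined |
|---|---|---|---|---|---|---|
| 0 | 1 | 0 | 1 | 1 | 0 | 1 |
| 0 | 5 | 0 | 5 | 5 | 0 | 5 |
| 1 | 1 | 1 | 1 | 2 | 0 | 2 |
| 1 | 5 | 1 | 5 | 6 | 0 | 6 |
| 1 | 10 | 1 | 10 | 11 | 0 | 11 |

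In an infant group of 162, with each event in a different child, the fourth row gives a SAR rate of 1/162 = 0.6% under Section 11.3 and 6/162 = 3.7% under Section 10.1.6.

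**4. Indeterminate events.** Section 10.1.6 creates this class. Section 3.1 counts only consistent events, so indeterminate events fall outside the primary count by definition. No section says how they are to be shown beside it. To see how far the primary count could thin out, take the Section 10.2 inputs (5%, n = 45) as the rate of events that would otherwise count, and let an assumed share q be classed indeterminate. The chance of at least one counted event is 1 − (1 − 0.05(1 − q))^45:

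| q | 0 | 0.10 | 0.25 | 0.50 | 0.75 |
|---|---|---|---|---|---|
| Chance | 0.90 | 0.87 | 0.82 | 0.68 | 0.43 |

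For a count that ignores causality, the chance stays at 0.90 for every q. The documents state no value of q.

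**The case against.** The best defence is that this is a drafting slip that the rest of the protocol corrects. Section 10.1.6 opens by referring to Section 3 for the endpoints, and Section 3.1 keeps the three categories apart. Seriousness is still decided by Section 11.1.3. AEs are also summarised by severity and relation to vaccination, so a related severe event stays visible as such. If the endpoint is read as one combined incidence, its value does not move. Safety is descriptive, so no formal conclusion depends on the label, and Section 10.1 leaves detail to a SAP finalised before database lock.

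Most of this stands, and it limits the effect to the separately reported SAR and severe AR rows. It does not remove the contradiction: a SAP written from this protocol would inherit two incompatible definitions of SAR.

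A reader might infer more from the treatment of indeterminate events. The documents do not support these stronger readings:

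- **That the trial would be blind to new signals.** Section 3.2 counts any SAE, any grade 3 AE and any IME regardless of causality. Section 10.1.6 requires tables and listings of severe or serious events with no causality filter. Section 13.11 plans narratives for SAEs and IMEs. The DSMB's escalation decisions use all solicited and unsolicited AEs and clinically significant laboratory values (Sections 4.1 and Synopsis).
- **That indeterminate events are the protocol's own potential signals.** Section 11.3 has a footnote to a category B1, "Potential signal and maybe considered for investigation", but the display it belongs to is not in the available text. Nothing there ties B1 to the indeterminate class.
- **That the primary count must include indeterminate events.** Restricting it to consistent events is an explicit choice in Section 3.1, not an error. Changing a co-primary definition after the DSMB has reviewed Stage I safety data (Section 1.2) would be a larger step than the problem warrants.

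**Conclusion.** The SAR sentence in Section 10.1.6 is wrong as written. It conflicts with Section 11.3, the abbreviation list, Section 11.2.2 and the separate naming of SAR and severe AR in Section 3.1. Followed literally, it inflates the SAR component by exactly the number of related non-serious severe AEs and empties the severe AR component by the same number.

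The combined SAR, severe AR and IMR count does not change, and neither does any test, error rate or sample size. The numerical size cannot be stated, because the documents give no rate of related grade 3 events; the figures 6 against 1 are illustrative.

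The treatment of indeterminate events is a gap in presentation. They are outside the primary count by definition but remain in the all-causality secondary endpoint and in the listings of severe or serious events. A supportive count is worth adding; a new primary definition is not needed.

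**What to change.** In Section 10.1.6, and in the SAP, replace the single SAR sentence with three assignments:

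- SAE classed as consistent: SAR.
- Non-serious grade 3 AE classed as consistent: severe AR.
- IME classed as consistent: IMR.

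Each event appears under its own heading. A non-serious grade 3 event can also be an IME, so state which heading it takes, so that a combined count includes it once.

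Keep the primary endpoint as consistent events only. Beside it, show indeterminate SAEs, severe AEs and IMEs by group, with a supportive total of consistent or indeterminate events.

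The cost is a few sentences and one table column. No new data are needed, because the algorithm already produces the indeterminate class, and the co-primary definition in Section 3.1 is untouched.

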#### ***Clinical Laboratory Tests***

Each continuous biochemistry and hematology laboratory test will be evaluated by means of descriptive statistics (i.e., number of subjects, mean, SD, median, minimum, and maximum) on the actual values, at each assessment time point and by group. Changes from baseline will also be summarized by assessment time point and by group. Relative changes in clinical laboratory test values compared to values at baseline will be evaluated according to Common Terminology Criteria for Adverse Events (CTCAE) version 4.0 (toxicity grades) or in accordance with the normal ranges of the clinical laboratory (below, within, or above normal range) for parameters for which no toxicity grades are defined.

A listing of subjects with any clinical laboratory test result outside the reference ranges will be provided.

#### **10.1.7 *Exploratory***

#### **10.1.8 *Viral sequencing methods***

Viral sequencing (e.g. deep sequencing) may be performed on selected stool samples taken at one or more of the time points specified in the Time and Events Schedule to explore the heterogeneity of shed virus, including reversion at known sites of attenuation, as well as attenuating modifications introduced to enhance genetic stability. Sequence information on shed virus may be compared with the results of neurovirulence testing, if available.

#### **10.1.9 *Missing Data***

The reasons for any missing data will be ascertained and appropriate statistical methods will be used to accommodate these absences in the analyses of trial data that minimize

potential biases and maximize efficiency conditional on the causes for data being missing. Data values that are identified by quality control procedures to be spurious will not be used in final analyses of trial data.

## 10.2 DETERMINATION OF SAMPLE SIZE

As in the historical control comparator study M2, this study has safety and Day 28 post-initial vaccination seroprotection rate as primary endpoints. Each age group will be monitored for safety; the primary immunogenicity endpoint, however will be limited to the infant groups **administered the 2018 lots of both vaccine candidates**, to which both 1- and 2-dose groups will contribute. The primary comparisons will entail comparisons of post-first-dose data from the four infant groups administered  $10^5$  and  $10^6$  dose levels of candidate 1 (2018) and candidate 2 (2018), to the corresponding infant cohort from study M2. **Data obtained for candidate 2 (2016) material will be summarized, and not involved in direct comparisons with the historical control.**

The sample size for the older children (**Groups A1H2[2018], A2H2[2016], and A2H2[2018]**) is chosen to provide adequate safety data prior to age de-escalation. Forty-five subjects are required to have 90% probability of observing at least one occurrence of an adverse event, when the true adverse event rate is 5%. Allowing for a 10% non-evaluability/dropout rate requires 50 subjects for the safety evaluations. Immunogenicity will be assessed as a secondary endpoint in the older cohort.

For the primary immunogenicity endpoint, it is assumed that the seroprotection rate following administration of a single dose of Sabin mOPV2 and **2018 lots of candidate nOPV2** vaccines in this population will be  $\geq 95\%$ . In the historical control comparator study, M2, a total of 91 per-protocol subjects (a 20% dropout rate from the enrolled population) were available for the immunogenicity endpoint in the younger cohort. For the current study, 129 evaluable (per-protocol) subjects per vaccine candidate and per dose level are required such that 90% power is available to declare non-inferiority to the Sabin 2 control, using the lower confidence bound of the Miettinen-Nurminen score confidence interval for inference (one-sided  $\alpha = 0.025$  for each candidate vaccine and dose level, separately, non-inferiority margin 10%). Therefore, assuming a 20% dropout rate the required enrollment is 162 subjects. Since the safety endpoint requires 50 subjects, and all subjects contribute to the immunogenicity endpoint, 50 randomly-chosen subjects will be assigned to receive two doses, and the remaining 112 subjects will receive only a single dose of each candidate vaccine.

**Sample sizes for the 2016 candidate 2 groups in Stage I were selected based on the same criteria, prior to availability of the 2018 material.**

Multiplicity is addressed in two ways. First, because there are two candidates, immunogenicity non-inferiority is assessed using the Bonferroni-corrected one-sided type I error rate of 0.025 (0.05/2). Second, multiplicity between dose levels for each candidate is addressed by considering fixed-sequence testing; that is, the  $10^6$  CCID50 dose will be tested for non-inferiority first at level  $\alpha = 0.025$ . If the non-inferiority criterion is met for a given vaccine candidate, the  $10^5$  CCID50 dose level will also be tested for non-inferiority at level  $\alpha = 0.025$  for that vaccine candidate.

## **11. ADVERSE EVENT REPORTING**

### **11.1 DEFINITIONS**

#### **11.1.1 *Adverse Events***

An Adverse Event Following Immunization (AEFI), has been defined by the working group on vaccine pharmacovigilance of the Council for International Organizations of Medical Sciences (CIOMS) and the World Health Organization (WHO), as “any untoward medical occurrence which follows immunization and which does not necessarily have a causal relationship with the usage of the vaccine. The adverse event may be any unfavorable or unintended sign, abnormal laboratory finding, symptom or disease”

An AEFI can therefore be any unfavorable and unintended sign (including an abnormal laboratory finding), symptom, or disease (new or exacerbated) temporally associated with the use of a vaccine product.

Examples of an AE include:

- Exacerbation of a chronic or intermittent pre-existing condition including either an increase in frequency and/or intensity of the condition.
- New conditions detected or diagnosed after vaccine administration even though they may have been present prior to the start of the study.
- Signs, symptoms, or the clinical sequelae of a suspected interaction.
- Signs, symptoms, or the clinical sequelae of a suspected overdose of either vaccine or a concurrent medication (overdose per se should not be reported as an AE/SAE).
- Signs, symptoms temporally associated with vaccine administration.
- Pre- or post-treatment events that occur as a result of protocol-mandated procedures (i.e. invasive procedures, modification of subject’s previous therapeutic regimen).

Solicited AEs are described in Section 11.1.2. All other AEs will be recorded as unsolicited AEs.

Examples of an AE DO NOT include:

- Medical or surgical procedures (e.g. endoscopy, appendectomy); the condition that leads to the procedure is an AE/SAE.
- Situations where an untoward medical occurrence did not occur (e.g. social and/or convenience admission to a hospital, admission for routine examination).
- Anticipated day-to-day fluctuations of pre-existing disease(s) or condition(s) present or detected at the start of the study that do not worsen.
- Pre-existing conditions or signs and/or symptoms present in a subject prior to the study vaccination. These events will be recorded in the medical history section of the CRF.

